Headsets will be cleaned and sanitized before being given to the patients.

To minimize the psychological risk of frustration or self-blame due to participants not experiencing reductions in their experience of pain, this possibility will be explicitly addressed during the consenting process. It will be emphasized that changes in the experience of pain will likely happen gradually, rather than all at once.

Additionally, participants will be guided during the VR-GI experiences to reduce their pain intensity, rather than turn off their pain entirely to appropriately set participants' expectations and to minimize the risk of frustration or self-blame. The extent of pain reduction visualized in VR-GI may be increased at the discretion of the participant throughout the intervention. Participants will be able to contact [name] or [name] during the intervention if they experience frustration or self-blame.

28. Risk/Benefit Analysis - Potential Benefits and Alternatives

28.1. Describe any potential for direct benefits to participants in the study: (check all that apply)

There are no direct benefits to research participants

Improvement in some or all of participants' symptoms

Improvement in some or all of participants' survival or longevity

Information gained from testing or monitoring procedures

Provision of drug or device

Reduced side effects

Other (explain below)

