Participants & Procedures: 36 chronic pain patients (18 with chronic back pain, CBP, and 18 with complex regional pain syndrome, CRPS) with no significant movement problems will be recruited from the USC Pain Center by referring physicians. Chronic pain will be defined as an average pain level of 5 or greater on a 0-to-10 pain intensity scale for greater than 3 months. Patients will be individually randomized to the VR-GI condition ($n = 24$, 12 CBP and 12 CRPS) or the audio-only GI active control condition ($n = 12$, 6 CBP and 6 CRPS). After informed consent and eligibility screening, all patients will complete pre-assessment questionnaires, an individual training session for completing VR-GI using the Limbix VR Kit or audio-only GI using an mp3 player, and their first session of GI. Patients will be instructed to practice GI at home once per day for 2 weeks. After 2 weeks, patients will be contacted to complete post-assessment questionnaires and a qualitative interview regarding intervention feasibility and acceptability. Referring physicians will also be informally interviewed regarding feasibility of integrating the intervention into their workflows. To ensure results are unbiased, a USC research coordinator with no commercial interest in the study outcome will conduct data collection.

Potential Problems: The Limbix team has extensive experience in product development and thus has first-hand knowledge of the problems that may be faced during the development of this product. Limbix has already solved many feasibility issues inherent in delivering a VR intervention for patients, as ascertained through extensive user research, via the development of the commercially available Limbix VR Kit. The usability and feasibility testing outlined above have been explicitly designed to expose issues early in the development process to help avoid unanticipated problems in product development.

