One potential issue we foresee is whether patients will comply with at-home GI practice. Tracking compliance via the VR Headset will allow for the evaluation of this possibility. If compliance is found to be an issue with early study participants, strategies could be employed to encourage compliance, such as sending reminders, discussing with patients how to better integrate practice into their daily routines, or having patients directly report daily practice to the research coordinator to increase accountability. Tracking compliance objectively, rather than relying on subjective report, will not be possible for the audio-only GI group. Though this represents a limitation in the study design, it nevertheless reflects an advantage of using VR for delivering GI. Another potential problem is that patients may not return loaned equipment. To limit this possibility, participants will be financially incentivized to return equipment at the conclusion of the study. Patients will receive the equipment by mail to their address along with a pre-paid envelope to return the equipment. Finally, participants will be asked to use online surveys to report pain ratings before and after at-home GI practice, requiring that they have internet access at home. We expect that this will not be problematic for most participants. If necessary, participants can keep written logs of daily practice.

12.2. Describe the statistical considerations for the study, how the sample size was determined, and how the results will be analyzed, if applicable. (Refer to specific sections of the protocol/grant, if applicable)

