To evaluate feasibility, outcomes of enrollment feasibility, intervention tolerability, and compliance will be qualitatively assessed. Additionally, confidence intervals will be calculated for each outcome measure using varying levels of confidence to evaluate the strength of preliminary evidence that the true value of the feasibility metric includes an 80% threshold. An 80% threshold for each outcome will be considered a conservative measure of feasibility. Feasibility and acceptability of the intervention will also be qualitatively evaluated based on post-assessment interviews with patients. Post-intervention patient interviews are expected to demonstrate that the at-home VR-GI intervention was feasible for patients to integrate into their daily routine, easy to use, and deemed acceptable and efficacious for pain management.

For efficacy measures, means, variability, and effect sizes for differences between pre- and post-intervention changes in pain intensity, pain medication use, functional outcomes, quality of life, and mood will be calculated. A confidence interval approach, using multiple levels of confidence to evaluate the strength of preliminary evidence, will be taken to evaluate whether the mean treatment difference is above zero and whether confidence intervals include a clinically important difference for each outcome. Pain intensity ratings will serve as the primary outcome measure in a follow-up Phase II clinical trial. The clinical significance for pain reduction will be considered 30%. For all other measures, clinical significance will be defined as a standardized effect size between 0.3 and 0.5.

Feasibility and efficacy measures will be descriptively compared between VR-GI and traditional audio-only GI. It is expected that feasibility of these two interventions will be comparable. Efficacy measures are expected to show larger effect sizes for the VR-GI experience. To evaluate the generalizability of VR-GI, whether there are notable differences in feasibility or efficacy between the two pain populations, CNBP and CRPS, using a confidence interval approach will also be evaluated. No such differences are anticipated. A larger subsequent Phase II randomized clinical trial will allow for

statistical comparisons between conditions (VR-GI and audio-only GI) and pain populations (CNBP and CRPS).

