Measures & Analyses: Feasibility outcome measures will include enrollment feasibility (i.e., proportion of recruited participants ineligible to participate and/or who decline to enroll), intervention tolerability (i.e., proportion of enrolled participants who discontinue intervention, are lost to follow-up, or experience adverse events), and compliance (i.e., proportion of at-home daily practice completed). Compliance can be tracked via the VR Headset, which will log the time and duration of practice. Measures of pain ratings, pain medication use, functional outcomes, quality of life, and mood will be collected before and after the 2-week intervention. Daily pain ratings before and after GI practice at home will be collected via online surveys. Patient feedback on ease of implementation, satisfaction with technology and content, expressed willingness to continue use, and enjoyment will be assessed via qualitative interview. These questions will be developed by [name] in collaboration with [name]. Due to the small sample size of this feasibility study, statistical analyses will not be prioritized. Instead, qualitative analysis and confidence interval approaches will be taken (see Protocol Synopsis) to evaluate feasibility of the VR-GI intervention and to prepare for a larger Phase II clinical trial to evaluate efficacy. Exploratory qualitative analyses will assess whether daily reported pain reductions habituate over time, whether one of the VR-GI prototypes was preferred over the other, whether VR-GI differentially affected CNBP and CRPS patients, and whether sex, ethnicity or race affected outcomes. All data analysis will be conducted by [name] and supervised by project PI.

18. Methods and Procedures - Device Information

This screen is required if you indicated the use of Approved or Investigational Devices (Question 9.2.)

18.1. Fill in an entry for each device that will be used in this study.

Generic and Brand Names	Category of Regulation
Limbix Virtual Reality Guided Imagery	Abbreviated IDE - nonsignificant risk device

18.2. Attach a copy of any Investigators Device Brochures for the devices listed above.

Name	Version Modified
Device Brochure(0.01)	0.01 7/15/2019 7:03 PM

18.3. Describe where the investigational devices will be stored, how they will be secured, and how the inventory will be managed.

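### Compliance would be compared between arms using a headset log for VR-GI and unspecified self-report for audio-only, with no analysis step for the difference

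*Combined protocol and SAP*

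**What the plan says.** Section 12.2 (Measures & Analyses) defines the metric once, without an arm-specific version: "compliance (i.e., proportion of at-home daily practice completed"). The one source it names is the device: "Compliance can be tracked via the VR Headset, which will log the time and duration of practice".

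Section 12.1 (Potential Problems) concedes that this does not carry over to the control arm: "Tracking compliance objectively, rather than relying on subjective report, will not be possible for the audio-only GI group". It calls this a limitation of the design and takes it no further.

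The statistical considerations in section 12.2 list compliance among the feasibility outcomes and then state: "Feasibility and efficacy measures will be descriptively compared between VR-GI and traditional audio-only GI". The expectation follows: "It is expected that feasibility of these two interventions will be comparable".

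The practice schedule is the same in both arms (section 12.1, Participants & Procedures): "Patients will be instructed to practice GI at home once per day for 2 weeks". Daily reporting is also planned without restriction by arm. Section 12.1 says "participants will be asked to use online surveys to report pain ratings before and after at-home GI practice", and section 12.2 repeats it: "Daily pain ratings before and after GI practice at home will be collected via online surveys". Written practice logs are a fallback where home internet is a problem. Reporting to the coordinator is something that could be added if compliance proves poor. None of these is named as the source of the compliance figure.

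**The concern.** One definition is to be filled from two kinds of data. A device log records whether the headset was used. Self-report records what the patient says was done, and it can count missed days as practised. If the two are tabulated side by side, a gap or a match between the arms may partly reflect the data source.

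The error can work in either direction for the reader. With equal true compliance, over-reporting in audio-only makes VR-GI look worse. With truly better compliance in VR-GI, the same over-reporting can make the arms look alike, which is the result the plan expects. A confidence interval does not reveal this, because the difference is systematic.

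What is at stake is how one descriptive table is read. The milestone in section 11.1 (Specific Aim 2) concerns VR-GI, which has the log. The enrollment and tolerability comparisons do not depend on the practice record.

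**Working it through.** **Step 1: which source feeds which arm.** The VR-GI source is the headset log (section 12.2). The audio-only arm uses an mp3 player and is said not to be objectively trackable (section 12.1). Subjective report is therefore implied for audio-only, but this is an inference, because the source is never stated. Section 12.2 gives no common measure, sensitivity analysis, separate reporting or reading rule for the difference.

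**Step 2: inputs.** From the documents: 24 VR-GI and 12 audio-only patients, and daily practice for 2 weeks, so 14 scheduled days. Assumed, because the documents give no values: true compliance *c*, the share *f* of missed days reported as done, the between-patient SD, and the within-patient correlation. The plan states no compliance rate or precision figure to reproduce.

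**Step 3: false gap when true compliance is equal.** Reported audio-only compliance = *c* + (1 − *c*) × *f*, so the false gap = (1 − *c*) × *f*.

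| True compliance | f = 10% | f = 20% | f = 30% |
|---|---|---|---|
| 60% | 4 points | 8 | 12 |
| 70% | 3 | 6 | 9 |
| 80% | 2 | 4 | 6 |
| 90% | 1 | 2 | 3 |

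At 70%, audio-only appears as 73%, 76% or 79% against a logged 70%. In days, that is 14 × 0.03 = 0.42 to 14 × 0.09 = 1.26.

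**Step 4: a hidden difference.** Suppose true compliance is 79% in VR-GI and 70% in audio-only, with *f* = 30%. Audio-only reports 0.70 + 0.30 × 0.30 = 0.79. The table shows 79% against 79%, and a true 9-point difference disappears.

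**Step 5: sampling error.** The 95% half-width for the difference in mean compliance is t(0.975, 34 df) × SD × √(1/24 + 1/12) = 2.032 × SD × 0.3536. For an SD of 15, 20 or 30 points this gives 10.8, 14.4 or 21.6 points. The 3 to 9 points at 70% compliance lie below all three.

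**Step 6: what a shared self-report count would leave.** At 70% true compliance in both arms, the remaining gap = 0.30 × (audio-only share − VR-GI share).
- Equal shares: 0 points.
- 10% in VR-GI, 30% in audio-only: 0.30 × 0.20 = 6 points.
- 0% in VR-GI, 30% in audio-only: 0.30 × 0.30 = 9 points, so no improvement.

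**Step 7: how well VR-GI can show the reporting error.** There are 24 × 14 = 336 scheduled days, of which 0.30 × 336 ≈ 101 are missed at 70% compliance, or 4.2 per patient. For an over-reporting share of 20%, the 95% half-width is 1.96 × √(0.20 × 0.80 / 101) = 7.8 points if days within a patient are independent. With the inflation factor √(1 + 3.2 × ICC), it is 10.9 points at an ICC of 0.3 and 12.6 at 0.5.

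Missed headset logging is not modelled. It would lower the VR-GI figure.

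**The case against.** The strongest reply is that the plan already says this. Section 12.1 states the limitation openly, the comparison is descriptive, formal testing is not prioritized, and statistical comparison of the conditions is left to Phase II. A gap of 3 to 9 points could not be interpreted with 12 control patients even with perfect measurement. The suggested remedy may also leave the whole gap if over-reporting differs by arm, and it replaces good VR-GI data with a proxy that partly measures survey completion. Finally, section 12.2 refers to a Protocol Synopsis, and section 21.2 lists a feasibility questionnaire whose content is not in the text. Either might name the audio-only source.

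Most of this is accurate and limits the weight of the point. It does not remove it. Disclosure does not tell the analyst which number goes in the audio-only cell or how to read it beside a logged one. Being below the sampling error does not make a systematic difference visible. The imperfect remedy applies only to the between-arm comparison, so the log is not given up where it matters. That an unseen attachment settles the source is possible, but nothing in the text indicates it.

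**Conclusion.** The point holds and is minor. The plan as written implies a comparison of logged practice with self-reported practice under one definition, with no designated audio-only instrument and no analysis step for the mismatch. The true size is unknown. Under assumed true compliance of 60% to 90% and over-reporting of 10% to 30% of missed days, the false gap is 1 to 12 points. At 70% it is 3 to 9 points, or about 0.4 to 1.3 days of 14. No decision rule, sample size or milestone changes.

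**What to change.** Add the following to section 12.2:

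- For the between-arm comparison only, compute compliance the same way in both arms. A day counts as practised if a post-practice survey rating exists for it, or a written-log entry where logs are used. Divide by the 14 scheduled at-home days.
- Keep the headset log as the measure for the VR-GI 80% milestone.
- Report survey-versus-log agreement within VR-GI as an indication of reporting error.
- State that any between-arm contrast of log against self-report is not like for like.

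The cost is wording only, because the daily surveys and written logs are already planned. There are three downsides. Practice without a survey or log entry is counted as missed. VR-GI will carry two compliance figures, which must be labelled. Reporting error may still differ by arm, and the agreement found in VR-GI may not transfer to audio-only.

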Specific Aim 2: Evaluate feasibility and usability of at-home VR-GI intervention in a 2-week clinical trial and prepare for larger subsequent clinical trial. 36 patients (chronic back pain or complex regional pain syndrome, CRPS) will be recruited to complete 1-2 online clinic training sessions followed by 2 weeks of daily at-home VR-GI (n = 24) or traditional audio-only GI (n = 12) practice. Intervention feasibility will be evaluated via questionnaires and via informal interviews with providers. Pre- and post-intervention measures of opioid use, pain ratings, functional outcomes, mood, and quality of life will be collected. Daily pre- and post-GI practice pain ratings will be collected to evaluate potential habituation effects of VR-GI over time. SA3 Milestone: Using a confidence interval approach, demonstrate that the VR-GI

intervention is feasible, defined as meeting an 80% threshold for feasibility metrics (i.e., enrollment feasibility, intervention tolerability, and compliance). Efficacy, defined as a 30% reduction in pain ratings and standardized effect sizes between 0.3- .05 on opioid use and other collected measures, will also be evaluated to prepare for a Phase II clinical trial.

11.2. Provide a summary of the background of the study, and explain how this research will contribute to existing knowledge. Describe previous work that provides a basis to show that the proposed research can be carried out without undue risk to human subjects. Include relevant citations. (Refer to specific sections of the protocol/grant, if applicable)

Public health impact of chronic pain

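### The feasibility milestone is to be demonstrated by confidence intervals, but the stated criterion, that 80% is included, shows only that 80% is not ruled out, and is easier to meet at higher confidence

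*Combined protocol and SAP*

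**What the plan says.** The milestone under Specific Aim 2 in section 11.1 reads "Using a confidence interval approach, demonstrate that the VR-GI" and continues "intervention is feasible, defined as meeting an 80% threshold for feasibility metrics (i.e., enrollment feasibility, intervention tolerability, and compliance".

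Section 12.2 describes the analysis. Feasibility metrics are assessed qualitatively, and in addition "confidence intervals will be calculated for each outcome measure using varying levels of confidence", the purpose being "to evaluate the strength of preliminary evidence that the true value of the feasibility metric includes an 80% threshold". The next sentence says "An 80% threshold for each outcome will be considered a conservative measure of feasibility".

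The efficacy paragraph of the same section uses a parallel construction. It asks whether the mean treatment difference exceeds zero and "whether confidence intervals include a clinically important difference for each outcome".

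The Measures & Analyses part of 12.2 says "qualitative analysis and confidence interval approaches will be taken (see Protocol Synopsis) to evaluate feasibility of the VR-GI intervention". No such synopsis can be identified in the text available. The same part defines enrollment feasibility as the "proportion of recruited participants ineligible to participate and/or who decline to enroll". It defines tolerability as the proportion who discontinue, are lost or have adverse events. Both are failure proportions.

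No confidence level, interval method or pass count is given for feasibility.

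**The concern.** A threshold that must be met, and that the authors call conservative, is naturally a floor: the success rate should be at least 80%. To demonstrate a floor with an interval, the lower limit has to reach it. Section 12.2 asks instead whether 80% is included. An interval that contains 80% is compatible with 80% and also with every lower value inside it.

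Intervals from the same data are nested, so raising the confidence level can only make inclusion easier. A reader who sees the criterion met at 99% would normally take that as the strictest evidence. Here it is the weakest requirement.

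Feasibility is the trial's main aim and the stated preparation for Phase II. The criterion as written would let results well below 80% be reported as supporting the milestone.

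**Working it through.** The plan states no feasibility figure (no pass count, power or interval width), so there is none to reproduce. The check asks what the criterion would accept.

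**Inputs from the plan.** The threshold is 80% (11.1 and 12.2). The VR-GI arm has n = 24, with 12 per pain diagnosis (12.1 and 12.2).

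**Assumptions not in the plan.** Tolerability is a binomial success proportion (the complement of the stated definition). Intervals are exact (Clopper-Pearson), two-sided, at 80, 90, 95 and 99%. Intervals wholly above 80% are also counted as meeting the criterion. This is the charitable reading, and under it the criterion becomes: upper limit ≥ 80%.

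**Step 1: lowest count that qualifies.** For x successes and level C, the upper limit is the (1+C)/2 quantile of Beta(x+1, n−x). The chance of qualifying is P(X ≥ lowest x) for X ~ Binomial(24, p).

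| Confidence | Lowest x | Observed rate | Interval for 15/24 | Chance at true 60% | Chance at true 70% |
|---|---|---|---|---|---|
| 80% | 17 | 70.8% | 47.4–75.9% | 19.2% | 56.5% |
| 90% | 16 | 66.7% | 43.7–78.8% | 32.8% | 72.5% |
| 95% | 15 | 62.5% | 40.6–81.2% | 48.9% | 84.7% |
| 99% | 14 | 58.3% | 34.7–85.4% | 65.0% | 92.6% |

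So 15/24 fails at the two lower levels and qualifies at the two higher ones.

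**Step 2: dependence on the interval method.** Wilson intervals give lowest counts of 17, 16, 16 and 15, and chances at a true 60% of 19, 33, 33 and 49%. The direction is the same.

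**Step 3: the literal reading.** If 80% must lie inside the interval, a perfect 24/24 (exact 95% interval 85.8–100%) does not qualify at 95%. This is a consequence of the wording, and the conclusion does not rest on it.

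**Step 4: what a lower-limit criterion would give.** The exact one-sided lower limit reaches 80% at level L when P(X ≥ x | n, p = 0.80) ≤ 1 − L. The highest such level is therefore P(X < x | n, p = 0.80).

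| x of 24 | 15 | 19 | 20 | 21 | 22 | 23 | 24 |
|---|---|---|---|---|---|---|---|
| Highest one-sided level | 1.3% | 34.4% | 54.0% | 73.6% | 88.6% | 96.7% | 99.5% |

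On this scale 15/24, which qualifies at 95% and 99% under the present wording, scores about 1%.

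**Step 5: compliance.** This metric has repeated sessions per patient. Assume 14 sessions each (24 × 14 = 336) and within-patient correlation ρ. The 95% half-width at 80% is 1.96 × √(0.8 × 0.2 × (1 + 13ρ)/336). That is 4.3 points for ρ = 0, 9.5 for ρ = 0.3 and 11.7 for ρ = 0.5. The plan gives no correlation, so these values only illustrate the range.

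**The case against.** The strongest reply is that section 12.2 never presents inclusion as a pass rule. It assesses the metrics qualitatively, adds intervals as preliminary evidence, and says formal testing is not prioritized. On that view the passing probabilities above belong to a rule the plan does not state. The plan also never says that inclusion at a higher level is stronger evidence. Reported side by side, a 15/24 result that misses at 80% and 90% and reaches 80% only at 95% would look weak to a careful reader. The wording may simply be loose, and the synopsis referred to may say something clearer. Finally, a lower-limit criterion amounts to a one-sided exact test and is hard to meet with 24 patients.

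Some of this stands. The sentence is loose, the passing probabilities depend on treating it as a criterion, and the lower limit is demanding. The mismatch remains. Section 11.1 says *demonstrate*, 12.2 offers only inclusion, and nothing else in the text requires a lower limit, or even a point estimate, to reach 80%. Because the plan sets testing aside in favor of intervals, the interval criterion carries the inference. Leaving the direction to the reader is part of the defect. If the synopsis holds a different rule, 12.2 should state it.

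**Conclusion.** The concern holds. Inclusion of 80% cannot demonstrate a success rate of at least 80%, whether or not intervals wholly above 80% also count. The reversal with confidence level follows from the nesting of intervals and holds for any standard interval method. Its size, with n = 24, exact intervals and a success-scale tolerability metric, is that observed rates as low as 62.5% at 95% confidence, or 58.3% at 99%, would be compatible with the criterion. The assumed levels and method affect the exact counts but not the direction. Reading the 80% as a floor is an inference from the word *meeting* and from its description as conservative. This should be fixed before the analysis. It does not affect the design or the data to be collected.

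**What to change.** In section 12.2, replace the inclusion wording with a directional criterion:

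1. Express enrollment and tolerability as success proportions, so that 80% is a floor for all three metrics.
2. Keep the several confidence levels, but grade each metric by the highest one-sided level at which the exact lower limit is at or above 80%.
3. Name in advance the one-sided level that counts as demonstration in 11.1, or change the milestone there to estimating feasibility.
4. Report a point estimate of 80% or more as descriptive only, with its interval. For example, 20/24 (83.3%) has an exact 95% interval of 62.6–95.3%.
5. Use a patient-level or clustered interval for compliance.

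The cost is about one paragraph of analysis text, with no new data. The drawback is a less favorable conclusion in many plausible cases. With a true rate of 90%, a one-sided 80% level (22 or more of 24) is reached 56% of the time and a one-sided 95% level (23 or more) 29%. With a true rate of 95%, the figures are 88% and 66%. In a VR-GI diagnosis subgroup of 12, even 12/12 reaches only 1 − 0.8^12 = 93%, so a one-sided 95% level is out of reach there. If that is too strict for a pilot, rewording the milestone as estimation is the simpler choice.
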